8.1.3. Sensitivity Analysis for Primary Endpoint

In the event that more than 10% of subjects do not complete the first 4 days of treatment (i.e. the period over which the primary endpoint is evaluated) or if there is a differential drop-out rate between the treatment groups, sensitivity analyses for primary endpoint will be performed using the following methods:

- a. Last observation carried forward (LOCF). If a subject has no further cold assessments after taking an alternative cough/cold medication (including acetaminophen/paracetamol), for subjects in the active group, subsequent symptom scores will be imputed with LOCF+1 (as per the additional sensitivity analysis described below).
- b. Control-based pattern imputation (Ratitch and O'Kelly 2011). The control-based pattern imputation will impute missing scores using available data from placebo subjects for each study day.

Additional sensitivity analyses will be performed whereby cold symptom assessments made within 4 hours after the use of any other cough/cold medication (including acetaminophen/paracetamol) are set to missing and the following imputation algorithm applied:

For subjects in the placebo group, individual symptom scores will be replaced using LOCF; for subjects in the active group, individual symptom scores will be replaced with LOCF+1. If the previous score for an individual symptom is 3 (maximum possible score), then LOCF will be used, as LOCF+1 would result in a value of 4, which is not possible. This imputation algorithm reflects the fact that the true cold symptom score, had alternative medication not been used, would have been at least as severe as the cold symptom score prior to the use of the alternative medication, and it is designed to ensure the imputed values do not introduce a bias in favor of the test product.

The sensitivity analyses will be performed based on the mITT population. Details of sensitivity analyses are provided in Appendix D.

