4.4.1. Intent-to-Treat (ITT) Population

Intent-to-Treat (ITT) population will consist of all randomized subjects.

In the event there is a discrepancy between treatment received and randomized treatment, all subjects in the ITT set will be analyzed according to the treatment they were randomized to receive and not according to what they actually received.

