4.4.2. Modified Intent-to-Treat (mITT) Population

The mITT population includes subjects who received at least one dose of study medication and have at least one post-baseline efficacy assessment. The mITT will be used for all primary, secondary and exploratory efficacy analyses.

In the event there is a discrepancy between treatment received and randomized treatment, all subjects in the mITT population will be analyzed according to the treatment they were randomized to receive and not according to what they actually received.

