4.4.4. Per Protocol (PP) Population

The Per-Protocol (PP) population will be determined from compliance during Days 1 to 4, since this is the period of the primary efficacy evaluation.

Any randomized subjects who violated the following inclusion or exclusion criteria will be reviewed on a case by case basis to determine whether they should be excluded from the PP population.

In addition, any subjects who violated the following criteria will be excluded from the PP population.

- a. Subjects who complete less than 80% or more than 120% of their target number of actuations over Days 1 to 4
- b. Subjects who miss 2 or more doses on any one day during Days 1 to 4
- c. Subjects who miss a total of 4 or more of their doses during Days 1 to 4

- d. Subjects who miss more than 1 nasal assessment on any one day during Days 1 to 4.
- e. Dosing outside of allowable time window (2 or more times on any day during Days 1-4)
- f. Use of prohibited medications during Days 1 to 4 as listed in the protocol
- g. Dosing more than 5 minutes prior to self-assessments of symptoms using the eDiary device at home. This is because dosing time is entered manually and can only allow entrance in the increments of 5 minutes. The manual time to be entered has to be in the past. Since the time for dosing has to be in the past and only in 5 minute increments, subjects may have entered a time for dosing that is earlier than automatic time for symptoms assessments.

Analysis on the PP population will be used as a supplement to the mITT analysis and will be performed for the primary efficacy endpoint average nasal symptom score Days 1-4 (ANSS₁₋₄) and the secondary efficacy endpoint average total symptom score Days 1-4 (ATSS₁₋₄).

5. Subject Disposition

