7.2.2. Treatment Compliance

Treatment compliance is assessed by the recording of dosing times and number of actuations in the subject e-diary. Treatment compliance for Days 1-4 and Days 1-7 will be

summarized descriptively (number of subjects and percentage) for <80% Compliance, 80-120% Compliance, >120% Compliance and by treatment group for the Safety population.

8. Efficacy Analysis

Efficacy analyses will be performed on both the mITT population and PP population. The primary endpoint average nasal symptom score Days 1-4 (ANSS₁₋₄) and secondary efficacy endpoint total symptom score Days 1-4 (ATSS₁₋₄) will be analyzed using the mITT population and PP population, all the other secondary and exploratory efficacy endpoints will be analyzed using the mITT population. The mITT analyses will be considered primary; the PP analyses will be considered supportive of the primary analyses on the mITT population.

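### The drop-out sensitivity analyses use mITT only, so randomised subjects with no post-baseline score enter no efficacy analysis

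*SAP*

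**What the plan says.** SAP 4.4.1 defines the widest set: "Intent-to-Treat (ITT) population will consist of all randomized subjects". SAP 4.4.2 defines the set used for efficacy: "The mITT population includes subjects who received at least one dose of study medication and have at least one post-baseline efficacy assessment". It then adds: "The mITT will be used for all primary, secondary and exploratory efficacy analyses".

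The opening of SAP Section 8 names the efficacy populations: "Efficacy analyses will be performed on both the mITT population and PP population". The PP analyses are supportive. After its definition, ITT appears only as a count in the disposition summary (SAP 5.1).

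SAP 8.1.3 plans LOCF and control-based imputation if "more than 10% of subjects do not complete the first 4 days of treatment", or if drop-out differs between the arms. It closes with "The sensitivity analyses will be performed based on the mITT population", which covers both methods. Protocol 9.2.5 uses the same trigger and leaves the details to the SAP, without fixing a population for these analyses. Protocol 9.3.2 assigns only the primary analysis to the modified ITT set.

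**The concern.** The drop-out analyses exist to show whether the result depends on who left. Membership of mITT itself depends on something that happens after randomisation, namely recording a score after the first dose. The subjects who leave soonest, with no later score, are therefore removed before the check begins.

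The design allows this to happen. In the schedule of events, randomisation comes before e-diary training, the baseline diary score, the nasal swab and the first dose. The next diary score falls just before the second dose, about 4 hours after the supervised first one. A subject can leave between randomisation and dosing, or stop after the first dose and make no further entry. Losses of the second kind could be related to the product, for example through nasal discomfort. If they were uneven between the arms, the comparison would no longer be between the groups as randomised, and the planned sensitivity analyses would not model the difference.

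**Working it through.** The plan gives no figure to reproduce here. The current N of 170 rests on the sizes of published studies, and the current text gives no expected drop-out rate, effect size or SD. The first step below is a comparison of sections; the others are arithmetic on stated assumptions.

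**1. Does any efficacy analysis include a subject with no post-baseline score?**

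| Set | Rule | Included? |
|---|---|---|
| mITT (SAP 4.4.2) | at least one dose and one post-baseline score | No |
| PP (SAP 4.4.4) | excludes "Subjects who miss more than 1 nasal assessment on any one day during Days 1 to 4" | No |
| ITT (SAP 4.4.1) | all randomised | Yes, but no efficacy analysis uses it |

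On PP: Day 1 has 4 assessments in the early stratum and 3 in the late stratum, and the first of each is the baseline. A subject with no later score misses 4 − 1 = 3 or 3 − 1 = 2 on Day 1 alone. Both exceed 1, so PP cannot recover the subject.

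**2. Who is affected?** Only subjects never dosed, or dosed with no later score of any kind. Someone who leaves on Day 2 with one later Day 1 score is in mITT and covered. The schedule also lists a diary self-assessment at the early-termination visit, which would give a returning subject a post-baseline score.

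**3. Could they be included?** A pre-dose baseline score normally exists, and SAP 4.1 uses the Screening value if it does not. The starting point for imputing Days 1–4 from placebo data is therefore available. The details of the control-based method in Appendix D are redacted, and nothing is inferred from them.

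**4. The trigger.** Neither document names the denominator. With 170 randomised, more than 10% means at least 18 non-completers (18/170 = 10.6%). Let m of those 18 have no post-baseline score (assumed). The mITT share is (18 − m)/(170 − m).

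| m | Share of the 18 left out | Counted among randomised | Counted in mITT |
|---|---|---|---|
| 1 | 6% | 10.6%, fires | 17/169 = 10.1%, fires |
| 2 | 11% | 10.6%, fires | 16/168 = 9.5%, does not fire |
| 5 | 28% | 10.6%, fires | 13/165 = 7.9%, does not fire |
| 8 | 44% | 10.6%, fires | 10/162 = 6.2%, does not fire |

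**5. Size of the effect of leaving them out.** Assume all m are in one arm of 85 and their mean ANSS1-4 differs from the rest by d SD. The shift in that arm's mean is d × m/85.

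| m | d = 0.25 | d = 1.0 |
|---|---|---|
| 1 | 0.003 SD | 0.012 SD |
| 5 | 0.015 SD | 0.059 SD |
| 8 | 0.024 SD | 0.094 SD |

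The standard error of the unadjusted difference at 85 per arm is √(2/85) = 0.153 SD. For five subjects the largest shift in the table is 0.059/0.153, about 0.4 of a standard error.

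**6. Dilution near the 17% criterion of protocol 9.2.3.** Assume a fraction f of the active arm has no post-baseline score and would follow the placebo course. The all-randomised reduction is then (1 − f) times the mITT reduction. A 17.0% reduction becomes 16.7% at f = 2%, 16.2% at f = 5% and 15.3% at f = 10%. At f = 5%, an mITT reduction between 17.0% and 17.0/0.95 = 17.9% falls below 17%. If f = 0 nothing changes. This describes dilution, and gives the same shrinkage when both arms lose equal numbers; it does not measure the effect of unequal loss.

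**The case against.** The strongest reply is that mITT is the prespecified primary population in both documents. Running the sensitivity analyses on the same set isolates the missing-data assumption from a change of population. That is a fair reason to keep mITT for the primary analysis and for LOCF. It does not explain why no analysis at all covers every randomised subject, and protocol 9.2.5 does not require the restriction.

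Three stronger readings are tempting, and the documents do not support them.

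- A reader might infer that these subjects count toward the trigger and are then left out of what it triggers. That is a natural reading of the unqualified word subjects, and disposition percentages do use the number randomised (SAP 5.1). But SAP 8.1.3 never says so, and the other 10% rule, in SAP 8.1.1, is counted in mITT explicitly. That contrast can be argued either way. What can be shown is that the denominator is missing.
- A reader might infer that an imbalance would go unseen. It would not. SAP 5.1 tabulates randomised, ITT, mITT and Safety counts by arm, with termination reasons. Dosed subjects are in the Safety population (SAP 4.4.3), and adverse events leading to withdrawal are listed (SAP 9.1.5). Only the effect on the estimate is not examined.
- A reader might infer that early drop-outs in general are omitted. Only those described in step 2 are.

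Two practical objections stand in part. The control-based analysis runs only if triggered. If 5% of the active arm alone were affected, that is 0.05 × 85 = 4.25 subjects, or 2.5% of 170, and the 10% limit would not be reached without other drop-outs. The alternative trigger, a differential rate, has no threshold. Also, the sensitivity p-values are nominal (SAP Section 4), so an ITT version would inform the 17% criterion without re-deciding it.

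**Conclusion.** The point holds in a limited form. On the current text, a randomised subject with no post-baseline score enters no efficacy analysis, including those planned to test drop-out. Counts by arm would be visible, but the effect on the estimate would not.

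The likely size is small. All the numbers rest on assumed values of m, d and f, because the documents give no expected number of such subjects, and there may be none. Even five lost from one arm shift its mean by at most about 0.06 SD over the range examined, against a standard error of about 0.15 SD. The 17% criterion would be affected only for a result close to it. The unstated trigger denominator is a separate small gap: with 18 non-completers, two with no post-baseline score are enough to change whether the analyses run.

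This is a cheap improvement. It does not show an error that would change the primary conclusion.

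**What to change.** Keep mITT for the primary analysis and for LOCF. In SAP 8.1.3, and in the matching part of Appendix D:

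- run the control-based imputation on the ITT population;
- for subjects with no post-baseline score, impute the Days 1–4 scores from placebo data given baseline NSS (Screening NSS if baseline is missing), center and Day 1 dosing-time stratum;
- state that the 10% and differential drop-out triggers are counted among all randomised subjects.

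The cost is a few sentences in the SAP and a little more programming. The exact edit to Appendix D depends on redacted text. The sensitivity estimate may come out slightly smaller. No new data or subjects are needed.

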8.1.4. Secondary Analysis for Primary Endpoint

If more than 20% of the symptom scores in the calculation of the ANSS₁₋₄ for an analysis population are missing, the summaries and analyses described for the ANSS₁₋₄ in Section 8.1.1 will be repeated for that analysis population on the ANSS₁₋₄ calculated without imputation of missing symptom scores (i.e. observed case analysis). The secondary analyses will be performed based on the mITT population.

In addition, the analysis described in Section 8.1.1 will be repeated for the PP population.

8.1.5. Adjustment of Covariates

All efficacy models will be adjusted by center and Day 1 dosing time stratification, and Baseline values.

8.2. Secondary Efficacy Endpoint

The secondary efficacy endpoints are (1) average nasal symptom score over Days 1 to 7 (ANSS₁₋₇), (2) average total symptom scores over Days 1 to 4 (ATSS₁₋₄), and (3) average total symptom scores over Days 1 to 7 (ATSS₁₋₇).

The ANSS₁₋₇, ATSS₁₋₄, and ATSS₁₋₇ will be summarized and analyzed in the same manner as ANSS₁₋₄. The ATSS₁₋₄, and ATSS₁₋₇, will also be analyzed using ANCOVA with a term included for treatment, treatment by Day 1 dosing time interaction, center and Day 1 dosing time stratification, and Baseline TSS (Day 1 prior to the first dose) as covariates. From this model, estimates of ATSS₁₋₄, and ATSS₁₋₇ for each dosing time strata will be obtained.

8.3. Other Efficacy Endpoints

8.3.1. Exploratory Analysis

The mean daily NSS (MDNSS) per study day will be derived as the mean of a subject's NSS scores per study day. The MDNSS and its change from baseline will be summarized by descriptive statistics by treatment group and day. NSS and MDNSS will be displayed graphically as line graphs showing the mean +/- SE within each treatment group over time.

Likewise, the mean daily total symptom score (MDTSS) per day will be calculated. The MDTSS and its change from baseline will be summarized by descriptive statistics by treatment group and day. TSS and MDTSS will be displayed graphically as line graphs showing the mean +/- SE within each treatment group over time.

Finally, for each symptom, the mean daily individual symptom scores (MDISS) per day will be calculated. The MDISS and change from baseline will be summarized by descriptive statistics by treatment group and day. Individual symptom scores and MDISS will be displayed graphically as line graphs showing the mean +/- SE within each treatment group over time.

The course of each of the 8 common cold symptoms across the treatment period will be summarized using frequency tables by treatment group and day.

9. Safety Analysis

Safety analyses will be summarized for the Safety population. All tables will be presented by treatment group.

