9.3.5.3. Exploratory Analysis

All exploratory analysis below will be done for the modified ITT population.

The mean daily NSS (MDNSS) per study day will be derived as the mean of a subject's NSS scores per study day. The MDNSS and its change from baseline will be summarized by descriptive statistics by treatment arm and day. NSS and MDNSS will be displayed graphically as line graphs showing the mean +/- SE within each treatment arm over time.

Likewise, the mean daily total symptom score (MDTSS) per day will be calculated. The MDTSS and its change from baseline will be summarized by descriptive statistics by treatment arm and day. TSS and MDTSS will be displayed graphically as line graphs showing the mean +/- SE within each treatment arm over time.

Finally, for each symptom, the mean daily individual symptom scores (MDISS) per day will be calculated. The MDISS and change from baseline will be summarized by descriptive statistics by treatment arm and day. Individual symptom scores and MDISS will be displayed graphically as line graphs showing the mean +/- SE within each treatment arm over time.

The course of each of the 8 common cold symptoms across the treatment period will be summarized using frequency tables by treatment arm and day.

Document Name	CCI	Protocol B_Final_Amendment 4_Clean_QA Review		
Type	Version	Document Identifier	Effective Date	
elido_clinical_doc	1.0; CURRENT; Most-Recent; Effective	090032d580d43d4b	19-May-2017 09:57:58	
Reason For Issue	Auto Issue			

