Study site personnel will dispense and train subjects on the e-diary and subjects will then perform their baseline self-assessment of common cold symptoms in their e-diary.

Study treatment will be administered via a nasal spray device (1 dose =3 actuations per nostril, each actuation is 140 μ L). Dosing administration is 3 actuations per nostril per dose, four times a day for 7 days (except for Day 1 where subjects in the 2nd strata will receive 3 doses). Subjects will be instructed to alternate nostrils after each actuation. First administration of study treatment will occur at the study site by independent site personnel supervision; first dosing can occur any time prior to 13:00.

Subject randomization will be stratified by dosing time on Day 1 by those study subjects receiving first dose of study treatment between the hours of: 8:00-11:00 and those receiving first dose of study treatment between the hours 11:01-13:00. On Day 1, subjects dosing between 8:00-11:00 will dose every 4 hours \pm 30 minutes for 4 doses and subjects dosing between 11:01-13:00 will dose every 4 hours \pm 30 minutes for 3 doses.

On Days 2-7 all subjects will administer their initial morning dose immediately following recording of their common cold symptom assessment at 07:00 \pm 2 hours and the remaining 3 doses every 4 hours \pm 30 minutes.

Dosing times and number of actuations will be recorded in the subject's e-diary. Subjects will be instructed not to take any additional cough/cold medications, including but not limited to, prescription, over-the-counter (OTC), non-drug/nutritional supplement, or procedures throughout the study. Subjects will be instructed to use acetaminophen/paracetamol over other OTC medications, but should try to avoid use if possible.

Subjects will self-evaluate the severity of the following common cold signs/symptoms before each dose and record their assessment in the e-diary: headache, muscle ache, chills, sore throat, blocked nose, runny nose, cough, and sneezing. Subjects will assess symptom severity on a 4-point scale (0=none, 1=mild, 2=moderate, 3=severe) at baseline and 4 times a day (except for Day 1 where subjects in the 2nd strata will receive 3 doses) through Day 7 immediately prior to each dose of nasal spray and record the scores in the e-diary. Safety will be assessed by occurrence of adverse events.

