4.1. Definition of Baseline and Study Day

Baseline is defined as the latest assessment prior to the first dose of treatment on Day 1, i.e., Day 1 Assessment 1. If a baseline measurement is missing or the subject receives the first dose prior to Day 1 Assessment 1, and a Screening value is available, the Screening value is utilized as the baseline. For assessments on or after Day 1, the study day will be calculated as assessment date – date of treatment (Day 1) + 1. For assessment prior to Day 1, the study day will be calculated as assessment date – date of treatment (Day 1).

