8.1. Primary Efficacy Endpoint

The primary efficacy endpoint is average nasal symptom score on Days 1 to 4 (ANSS₁₋₄). At each assessment, the individual nasal symptom scores will be summed to provide the NSS. On each day, the NSS scores at each assessment (excluding the baseline NSS on Day 1) will be averaged (mean) to provide a daily NSS. A subject's ANSS₁₋₄ is calculated as the mean of these daily NSS across study Days 1 to 4.

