Appendix A. Schedule of Events

SCHEDULE OF EVENTS

PROCEDURE	VISIT 1 (Day 1)		AT HOME PROCEDURES (Days 2-7)	VISIT 2 (Day 8) ^a
	Screening	Treatment Phase		End of study or early termination
Written informed consent	X			
Demographic data	X			
Medical history	X			
Record prior & concomitant medications and non-drug treatments/ procedures	X	X	X	X
Common cold symptom assessment ^b	X			
Vital signs ^c	X			X
Physical examination	X			X
Nasal examination	X			X
Urine drug screen	X			
Urine pregnancy test ^d	X			X
Inclusion/exclusion criteria	X			
RANDOMIZATION^e	X			
Dispense & train subjects on e-diary		X		
Self-assessment of common cold symptoms in subject e-diary ^f		X	X	X
Nasal swab sample ^g		X		
Instruct subjects on proper use of study treatment ^h		X		
Dispense & prime 1 st study device		X		
Study treatment administration ⁱ		X	X	
Collect subject e-diary				X
SAE and AE assessment and recording ^j	X	X	X	X
Study conclusion ^k				X

^a Subjects who discontinue study treatment before completing the study and those who prematurely withdraw from the study for any reason should undergo end of study visit procedures in-clinic as soon as possible.

^b Subjects will self-evaluate and grade their common cold symptoms using a 4-point scale (See Section 6.1.7. for more details). Only subjects meeting all eligibility criteria including the following criteria will be enrolled into the study:

1. A confirmed common cold diagnosis with symptoms $\leq 48-72$ hours;

2. TSS ≥ 9 (baseline sum of the 8 common cold symptoms described in Section 6.1.7.);

3. Score ≥ 1 for at least one of the following symptoms: sore throat, runny nose, or blocked nose.

The Investigator will confirm a common cold diagnosis. This will be collected in the case report form (CRF).

- c. Vitals will include blood pressure, pulse rate, respiratory rate, oral body temperature and height and weight measurements. Height and weight will only be collected during Screening.
- d. Only female subjects of childbearing potential.
- e. Site staff will stratify and randomize eligible subjects to one of the two treatment arms by contacting interactive response technology (IRT).
- f. Self-assessment of common cold symptoms using a 4-point scale (See Section 6.1.7. for more details) will be recorded in the subject e-diary immediately prior to the first dose at Baseline, immediately prior to each subsequent dose, and the morning of Day 8 upon awakening.

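### Read literally, SAP 8.3.1 puts the pre-dose baseline into the Day 1 mean daily scores, shrinking the exploratory Day 1 change from baseline by a quarter or a third

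*SAP*

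**What the plan says.** SAP 8.3.1 (Exploratory Analysis) defines the daily mean as follows: "The mean daily NSS (MDNSS) per study day will be derived as the mean of a subject's NSS scores per study day". It derives MDTSS likewise and MDISS in the same way for each symptom. Each mean and its change from baseline are to be summarised by treatment group and day and drawn as line graphs. Protocol 9.3.5.3 gives the same definition. Neither section says how the Day 1 baseline score is handled in the mean, and neither refers back to the primary endpoint's derivation.

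The primary endpoint is explicit. Under SAP 8.1, on each day "the NSS scores at each assessment (excluding the baseline NSS on Day 1) will be averaged" to give a daily NSS. Protocol 9.2.3 and 9.3.2 agree.

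SAP 4.1 fixes where baseline falls: "Baseline is defined as the latest assessment prior to the first dose of treatment on Day 1, i.e., Day 1 Assessment 1". It also says: "For assessments on or after Day 1, the study day will be calculated as assessment date" minus the date of treatment, plus 1. The baseline assessment therefore has study day 1. Note f of the Schedule of Events (SAP Appendix A) times the diary entries "immediately prior to the first dose at Baseline, immediately prior to each subsequent dose", with one more on the morning of Day 8.

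**The concern.** The plan has two daily nasal scores with nearly the same name. One leaves out the Day 1 baseline; the other, as worded, takes it in. A programmer who follows 8.3.1 to the letter would average the pre-dose score with the post-dose scores of Day 1 and then subtract that same pre-dose score. One term of the resulting change is zero whatever the treatment does.

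What is at stake is the first point of the displayed time course. The Day 1 change, and any early separation of the arms, would look smaller than it was, and by a different factor in each dosing-time stratum. A subject's four MDNSS values for Days 1-4 would also not average to that subject's ANSS1-4.

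**Working it through.** **Inputs**

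- Assessments: one before each dose, the first on Day 1 being the baseline (SAP Appendix A, note f; SAP 4.1).
- Day 1 doses: 4 for first dosing at 8:00-11:00, 3 for 11:01-13:00 (SAP 3.1).
- Days 2-7: 4 doses a day. One dose is 3 actuations in each nostril, so 6.

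**Reproducing the plan's own figures.** SAP 7.2.1 gives target actuations, which confirm the Day 1 dose counts and hence the number of pre-dose assessments:

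- Days 1-4: 6 x (4 + 12) = 96 and 6 x (3 + 12) = 90.
- Days 1-7: 6 x (4 + 24) = 168 and 6 x (3 + 24) = 162.

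All four match. Day 1 therefore has k = 4 scores (1 baseline, 3 post-dose) or k = 3 scores (1 baseline, 2 post-dose).

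**Day 1 change from baseline.** Let B be the baseline score and P the mean of the post-dose Day 1 scores.

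- Baseline excluded, as in SAP 8.1: change = P - B.
- Baseline included, as 8.3.1 reads: mean = [B + (k - 1)P]/k, so change = [(k - 1)/k](P - B).
- k = 4: factor 3/4 = 0.75, a shrinkage of 25%.
- k = 3: factor 2/3 = 0.67, a shrinkage of 33%.

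Illustration with B = 6 and P = 5 (invented values): the change is -1.00 with baseline excluded. With baseline included it is (6 + 15)/4 - 6 = -0.75, or (6 + 10)/3 - 6 = -0.67.

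Pooled over strata with the same change in each, the shrinkage lies between 25% and 33%, depending on the mix. At an assumed 50:50 split it is (0.25 + 0.333)/2 = 29.2%.

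**Difference between arms on Day 1.** Within a stratum, the factor (k - 1)/k applies exactly to the arm difference in change from baseline. For the raw Day 1 MDNSS it applies in expectation only, because a chance baseline imbalance would enter the mean with weight 1/k.

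**Gap to ANSS1-4.** For a subject with all four days, only the Day 1 term differs:

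- ([B + (k - 1)P]/k - P)/4 = (B - P)/(4k).
- In size this is 1/16 of the Day 1 change for k = 4 and 1/12 for k = 3. In the illustration: 0.0625 and 0.0833 points.

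**Sensitivity to the inputs.** If one post-dose Day 1 score is missing and not imputed, the baseline's weight rises from 1/4 to 1/3, or from 1/3 to 1/2. If the Screening value serves as baseline (allowed by SAP 4.1), the factors change for that subject.

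**The case against.** The strongest reply is that 8.3.1 is silent, not wrong. SAP 8.1 has already said how to form a daily NSS, and a programmer asked for a change from baseline might well carry that rule over. This stands in part: a reader might infer that the plan states that baseline is included, and no section does. Inclusion follows from the missing exclusion together with the baseline and study-day definitions. But 8.3.1 introduces a separately named variable with its own derivation and no cross-reference, and taken literally that derivation gives the diluted result.

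Second, the consequences are limited. That stands. The outputs are descriptive, with no test planned on MDNSS, MDTSS or MDISS. SAP 8.3.1 also plots the unaveraged NSS, TSS and individual symptom scores over time. Randomisation is stratified by dosing time, so the stratum mix should be similar in both arms, and the unequal factors create no expected difference between them.

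Third, the mismatch with ANSS1-4 is small for each subject. At group level, daily means need not average to the reported ANSS1-4 anyway: data after dropout are not imputed (SAP 8.1.2) and the primary comparison is covariate-adjusted (SAP 8.1.1). That also stands.

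Fourth, SAP 3.1 describes scoring at baseline and four times a day, which could mean baseline plus four further scores. The weights would then be 1/5 and 1/4. SAP 4.1 and Appendix A make the score before the first dose both the baseline and Assessment 1, which favours 1/4 and 1/3.

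Finally, a reader might extend the point to the secondary endpoints ATSS1-4 and ATSS1-7. The documents do not support that as a defect. Protocol 9.3.3 introduces them with a likewise, building them from daily TSS, and SAP 8.2 analyses them in the same manner as ANSS1-4. The exclusion is not repeated for TSS, but it is reasonably carried over.

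**Conclusion.** The point holds as a wording fault in an exploratory derivation. Followed literally, SAP 8.3.1 multiplies the Day 1 change from baseline by 0.75 or 0.67, according to dosing-time stratum. The Day 1 difference between arms shrinks by the same factor in expectation. These factors assume complete Day 1 data and Assessment 1 as baseline.

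It would be too strong to say that the trial's efficacy result is biased. Days 2-7 are unaffected, and so is the primary ANSS1-4 test, whose derivation excludes the baseline explicitly. The matter is minor but worth correcting, because the rule as written gives a diluted Day 1 figure in planned tables and graphs.

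**What to change.** In SAP 8.3.1, add to the MDNSS, MDTSS and MDISS definitions a clause such as *excluding the baseline score on Day 1*. Show baseline as its own point in the line graphs, so that no information is lost.

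The cost is one clause, to be added before unblinding. Protocol 9.3 leaves additional analysis detail to the SAP, so Protocol 9.3.5.3 need not be amended. Repeating the clause for the daily TSS behind ATSS1-4 and ATSS1-7 is optional tidying.
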